#### **Definitions**

**Liver-related death** as defined in Asrani et al. (Gastroenterology. 2013;145:375–82.e1–2): death with any of the following causes identified.

Disease category	ICD-10 codes			
Hepatitis C virus	B171, B182			
Other hepatitis	B15, B16, B170, B172, B178, B179, B180, B181, B188, B189, B19, K73			
Primary liver cancer	C22			
Secondary liver cancer	C787			
Esophageal varices	185			
Alcoholic liver disease	K70			
Hepatic failure	K72			
Liver cirrhosis	K74			
Other diseases of liver (toxic, inflammatory, and others)	K71, K75, K76			

**Significant rebleeding** will be defined by Baveno criteria as a recurrent melena or hematemesis resulting in any of the following:

- Hospital admission
- Blood transfusion
- 3 g/dL drop in hemoglobin.

**Bacterial infection:** hospitalization for bacterial infection by the specified time point

**Jaundice**: defined as total bilirubin > 50 μmol/L

Ascites: persistent ascites at the specified timepoint.

**Spontaneous bacterial peritonitis:** defined by an ascitic fluid polymorphonucleated (PMN) cell count of  $\geq 250$ /mm.

**Hepatic encephalopathy** (HE): HE is a brain dysfunction caused by liver insufficiency and portosystemic shunting. HE produces a wide spectrum of nonspecific neurological and psychiatric manifestations. Clinical HE is grading according to the West-Haven criteria.

**Hepatorenal syndrome** (HRS) is essentially a diagnosis of exclusion (i.e., there is an absence of other identifiable causes of renal failure). The hepatorenal syndrome is characterized by the following features in a patient who has established or clinically evident chronic liver disease:

i. diagnosis of cirrhosis and ascites;

- ii. diagnosis of AKI according to ICA-AKI criteria: increase of at least 0.3 mg/dL (26  $\mu$ mol/L) and/or  $\geq$  50% from baseline, within 48 h;
- iii. no response after 2 consecutive days of diuretic withdrawal and plasma volume expansion with albumin (1 g/kg of body weight);
- iv. absence of shock;
- v. no current or recent use of nephrotoxic drugs (non-steroidal anti-inflammatory drugs, aminoglycosides, iodinated contrast media, etc.);
- vi. and no macroscopic signs of structural kidney injury, defined as absence of proteinuria (> 500 mg/d), absence of microhematuria (> 50 red blood cells per high power field) and normal findings on renal ultrasound.

**Further decompensation** as defined in the Baveno VII conference: a second (or recurrent) portal hypertension-driven decompensating event (ascites, variceal hemorrhage, or hepatic encephalopathy) and/or jaundice, or the development of spontaneous bacterial peritonitis (SBP) and/or hepatorenal syndrome (HRS-AKI).

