#### **Secondary objectives:**

Demonstrate the efficacy of an "early-TIPS" strategy to reduce:

- 1/ All-cause mortality rate at Days 42 and 365.
- 2/ Liver related mortality rate at Days 42, 90, 180 and 365.
- 3/ Rebleeding rate at Days 42, 90, 180 and 365.
- 4/ Cumulative incidence of complications of cirrhosis at Day 365.
- 5/ Transfusion requirements at Days 42 and 365.

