#### **Secondary endpoints**

- 1- Survival at Days 42, 90, 180 and 365.
- 2- Incidence of liver related death at Days 42, 90, 180 and 365.
- 3- Incidence of significant rebleeding at Days 42, 90, 180 and 365.
- 4- Cumulative number of packed red blood cells required by each treatment arms.
- 5- Incidence of complications of cirrhosis during the 12-month follow-up.
- any of the complication below
- bacterial infections,
- jaundice,
- ascites.
- spontaneous bacterial peritonitis,
- hepatic encephalopathy,
- hepatorenal syndrome,
- further decompensation.
- 6- Frequency of:
- TIPS technical failure and TIPS complications: thrombosis, heart failure, infection and encephalopathy.

- Technical failure of GO and complications of GO: migration of glue, infection of the site of injection, significant bleeding during the procedure (hospital stay, blood transfusion, 3 g drop in hemoglobin).
- 7- Number of patients lost to follow up at Day 365 in each group
- 8- Change of MELD score between inclusion and Day 180 in each group.
- 9- Number of days spent in hospital in each group during the 12-months follow-up.
- 10- Number of bacterial infections and localizations.

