#### *Incidence of rebleeding during follow-up*

The association of study arms with rebleeding hazard function will be tested using univariate and multivariate Cox models. The cumulative risk of rebleeding during follow-up in each arm will be estimated by calculating the cumulative incidence function (CIF) rebleeding at 12 months. In this approach, death free of rebleeding during follow-up will be considered as a competing event.

Incidence of the other complications of liver cirrhosis during follow-up

The association of treatment group with the hazard function of other complications will be tested using univariate and multivariate Cox models. The cumulative risk of other complications during follow-up in each arm will be estimated by calculating the CIF at 12 months. In this approach, death free of complications during follow-up will be considered as a competing event.

Cumulative number of packed red blood cells required by each treatment arms.

Variation of MELD score between inclusion and 6 months in each arm

Number of days that patients spend in hospital during follow-up

Comparison between strategy groups will be performed with Student's t-test or the Mann-Whitney test, as appropriate.

Frequency of TIPS technical failure and TIPS complications: thrombosis, heart failure, infection and encephalopathy. Frequency of technical failure of GO and complications of GO: migration of glue, infection of the site of injection, significant bleeding during the procedure (hospital stay, blood transfusion, 3 g drop in hemoglobin).

This analysis will be performed on the safety population.

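### The definition of significant rebleeding omits death, so a recurrent bleed that kills before any listed consequence would be analysed as a competing death and understate rebleeding incidence

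*SAP*

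**What the plan says.** In section 6.1 (Definitions), the SAP says that significant rebleeding "will be defined by Baveno criteria as a recurrent melena or hematemesis resulting in any of the following". Three consequences follow:

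- "Hospital admission"
- "Blood transfusion"
- "3 g/dL drop in hemoglobin"

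Nothing else in the SAP adds to this list. The primary endpoint widens the source of bleeding to any upper gastrointestinal origin, but still requires the bleed to be clinically significant.

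The definition feeds secondary endpoint 3, "Incidence of significant rebleeding at Days 42, 90, 180 and 365". The matching secondary objective, "Rebleeding rate at Days 42, 90, 180 and 365", is among those for which the trial sets out to show a reduction with early TIPS.

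Section 6.2 gives the analysis: "The association of study arms with rebleeding hazard function will be tested using univariate and multivariate Cox models". It adds a cumulative incidence function at 12 months, in which "death free of rebleeding during follow-up will be considered as a competing event".

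**The concern.** A bleed has to lead to one of three things before it counts. A patient who has a recurrent haematemesis and dies before being admitted, transfused or having a qualifying haemoglobin fall documented meets none of them. That patient then has no significant rebleed on record, and the death goes to the competing column. The most severe form of the event that TIPS is meant to prevent would be left out of the endpoint that measures it. The competing-death curve would also contain bleeding deaths and could not be read as non-bleeding mortality.

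The route is not confined to deaths at home. Patients are randomised soon after the first endoscopy, and the subgroup table refers to an initial hospitalisation. For someone still in that stay, a new bleed does not naturally lead to an admission, so only transfusion or a measured haemoglobin fall remains. Most inpatients would probably meet one of these; a very rapid fatal bleed might not.

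**Working it through.** The SAP gives no figure on this point, so there is nothing to reproduce. The check compares the definition with the analysis rule and then sizes the effect.

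**Step 1: classification of a rapidly fatal recurrent bleed, as written**

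| Place in the SAP | Rule | Result |
|---|---|---|
| 6.1, primary endpoint | all-cause death or significant rebleeding | counted as an event (death) |
| 6.1, secondary endpoint 1 | survival | counted (death) |
| 6.1, Definitions, and secondary endpoint 3 | bleed plus one of three consequences | not a significant rebleed |
| 6.2, rebleeding, cumulative incidence | death without rebleeding competes | competing event, on the ordinary reading |
| 6.2, rebleeding, Cox model | handling of death not stated | censored at death, on the ordinary reading |

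**Step 2: effect of one such patient.** Input: 52 patients per arm (section 3.3). With full follow-up and no censoring, moving k patients out of the rebleeding event lowers that arm's 12-month incidence by k/52:

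- k = 1: 1/52 = 1.9 points
- k = 2: 2/52 = 3.8 points
- k = 3: 3/52 = 5.8 points
- k = 4: 4/52 = 7.7 points

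The values of k are assumptions.

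**Step 3: effect on the comparison of arms.** Inputs from section 3.3: composite failure of 40% (glue) and 15% (TIPS) at 12 months. Two assumptions are not in the SAP: 70% of composite events are rebleeds, and 5% to 15% of rebleeds, the same fraction in both arms, kill before any listed consequence.

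- Rebleeds, glue: 52 × 0.40 × 0.70 = 14.56. TIPS: 52 × 0.15 × 0.70 = 5.46.
- Patients lost, glue: 14.56 × 0.05 = 0.7 to 14.56 × 0.15 = 2.2, or 1.4 to 4.2 points of incidence. TIPS: 5.46 × 0.05 = 0.3 to 5.46 × 0.15 = 0.8, or 0.5 to 1.6 points.
- Ratio before: 14.56 / 5.46 = 2.67. After a 15% loss: 12.38 / 4.64 = 2.67.
- Absolute difference before: (14.56 − 5.46) / 52 = 17.5 points. After a 5% loss: 17.5 × 0.95 = 16.6. After a 15% loss: 17.5 × 0.85 = 14.9.

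An equal proportional loss multiplies both arms by the same factor. The ratio of rebleeds is unchanged, and so, approximately, is the Cox hazard ratio; the absolute difference shrinks.

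**The case against.** Four arguments can be made against the point.

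1. *The competing-event rule does not repeat the word significant.* A patient who dies of a witnessed haematemesis is not plainly free of rebleeding, so one could say the classification is merely unspecified. This has some force. However, endpoint 3 is expressly significant rebleeding, and the only definition supplied is the closed list. An analyst who programs that list will not count the patient. A competing event is also not the same as remaining event-free; the loss is from the rebleeding curve only.

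2. *The trial comparison is not shown to be biased.* A reader might infer that, because more rebleeds are expected with glue, the omission must distort the hazard ratio. The document does not support that. More missed events in the arm that rebleeds more is what an equal proportional loss produces, and such a loss leaves the ratio at about 2.67. Distortion would need a different rapidly fatal fraction in each arm, and nothing in the SAP indicates one. This objection stands in full.

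3. *The number of patients may be nil.* The case requires known melena or haematemesis, death, and none of the three consequences. The low end of the illustration is under one patient per arm. This also stands.

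4. *The definition invokes the Baveno criteria.* Whether that source lists death cannot be checked here and carries no weight either way. The SAP writes out its own list.

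**Conclusion.** The point holds as a defect in the definition of a secondary efficacy endpoint. A rule the SAP states would put a fatal recurrent bleed in the wrong category, which goes beyond missing detail.

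The size is about 1.9 percentage points of 12-month rebleeding incidence per patient affected, assuming 52 per arm with full follow-up. Within an arm the direction is certain: incidence can only be understated. Under an equal proportional loss in both arms, the absolute difference shrinks against TIPS (from 17.5 to between 14.9 and 16.6 points in the illustration) and the hazard ratio is roughly unchanged. Those figures rest on the assumed 70% and 5% to 15%; the count of such deaths is unknown and may be zero.

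A reader might also infer that the primary result is at risk. It is not: all-cause death is part of the composite, so these patients remain primary events, and overall survival counts them too. Sample size, power and alpha are untouched.

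**What to change.** Two edits, made before database lock:

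- In section 6.1, add death as a fourth consequence in the list, so that a recurrent melena or haematemesis resulting in death is a significant rebleed, dated at the bleed.
- In section 6.2, under rebleeding, state that only deaths neither preceded by, nor resulting from, a recurrent bleed meeting this definition are competing events. Use the same rule in the Cox model and the cumulative incidence function.

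The text change is short, but it has a cost. Someone must judge whether a death resulted from the bleed, and the trial is open label. The cause-of-death codes for liver-related death will not settle this alone: the table has a row for esophageal varices but none for gastric varices or gastrointestinal haemorrhage, so a bleeding death filed under cirrhosis would not be recognisable. The rule should therefore be applied from the event narrative.

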## **Section 5: Trial Population**

## **5.1 Eligibility**

**Inclusion criteria:** 

- Age  $\geq$  18 and  $\leq$  75 years.
- Cirrhotic patients with variceal bleeding from gastroesophageal gastric varices type 2 or isolated gastric varices type 1 or 2 (Sarin classification) according to the following criteria: endoscopic signs of an active spurting or oozing from gastric varices (GV); adherent blood clots, white nipple signs, or erosions on the GV and absence of other bleeding sources. Cirrhosis: The diagnosis of liver cirrhosis is based on previous liver biopsy or on the combination of clinical, biochemical, and radiological findings. If biopsy findings are unavailable and in case of non-complicated cirrhosis, non-invasive markers will be used.
- Hemodynamically stable patient without clinically significant rebleeding (Baveno criteria) within 12 hours after the initial endoscopy with glue obliteration.
- Written informed consent obtained.
- Patient affiliated to a social security system.

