## **Section 6: Analysis**

#### 6.1 Outcome Definition

## Primary endpoint

Death (all cause) or clinically significant rebleeding (upper gastrointestinal bleeding whatever its origin, with event date) during the one-year follow-up.

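### A variceal rebleed alone satisfies the any-complication line of secondary endpoint 5, through further decompensation, so that line can favour TIPS without any effect on non-bleeding complications

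*SAP*

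**What the plan says.** SAP section 6.1, Secondary endpoints, item 5 is the incidence of complications of cirrhosis over 12 months. Its first line is a composite, "any of the complication below". Seven items follow: bacterial infection, jaundice, ascites, SBP, hepatic encephalopathy, hepatorenal syndrome and "further decompensation". Variceal bleeding is not listed by name.

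The Definitions in the same section describe further decompensation as "a second (or recurrent) portal hypertension-driven decompensating event (ascites, variceal hemorrhage, or hepatic encephalopathy) and/or jaundice". New SBP and hepatorenal syndrome also count under that definition.

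Section 5.1 requires a variceal bleed at entry: "Cirrhotic patients with variceal bleeding from gastroesophageal gastric varices type 2 or isolated gastric varices type 1 or 2".

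Section 6.2 deals with rebleeding first. It then has a separate analysis titled "Incidence of the other complications of liver cirrhosis during follow-up", using Cox models and cumulative incidence functions, in which "death free of complications during follow-up will be considered as a competing event". It gives no rule for rebleeding there.

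Rebleeding is counted in two other places. The primary endpoint is death or "clinically significant rebleeding (upper gastrointestinal bleeding whatever its origin, with event date"), and significant rebleeding is secondary endpoint 3.

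**The concern.** Secondary objective 4 asks whether early TIPS reduces complications of cirrhosis. The reader of that result will want to know what TIPS does beyond preventing bleeding, above all for encephalopathy. The SAP background reports that in the one earlier randomized trial TIPS reduced rebleeding but carried a high risk of encephalopathy. It adds that recent studies of early covered stents found no difference in encephalopathy. A composite that combines an expected benefit, already counted twice elsewhere, with a possible harm answers that question poorly. It can favour TIPS when non-bleeding complications are equal, and it can look neutral when they are more frequent with TIPS.

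**Working it through.** **Step 1: does a rebleed alone meet the composite?**
- Any one listed item meets the composite, and further decompensation is a listed item.
- A second or recurrent variceal hemorrhage is further decompensation.
- The index event is a variceal bleed in every patient, so any later variceal bleed is recurrent.
- Nothing in sections 6.1 or 6.2 removes it. A variceal rebleed alone therefore meets the composite.

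**Step 2: what does further decompensation add to the list?** Ascites, encephalopathy, jaundice, SBP and hepatorenal syndrome are already listed. The ascites item, however, is restricted to ascites that persists at the timepoint, while further decompensation has no such condition. The main additions are therefore variceal rebleeding and non-persistent ascites.

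**Step 3: how large could the effect be?** The SAP states no complication rates, so this is an illustration and there is no figure of the plan's to reproduce.

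Inputs:
- r, the 12-month variceal rebleeding risk. The first pair, 40% glue versus 15% TIPS, is the composite failure rate in section 3.3. It is a ceiling for each arm, because that composite also counts deaths and non-variceal bleeding. The pairs 30% versus 10% and 20% versus 5% are assumptions.
- q, the 12-month risk of non-bleeding complications: assumed.
- Independence of the two: assumed.
- 52 patients per arm (section 3.3) and two-sided 0.05 (section 4.1).

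Formulas: risk of any complication = 1 − (1 − q)(1 − r); HR = ln(1 − risk TIPS) / ln(1 − risk glue). Worked example with q = 40% in both arms and r = 40% versus 15%:
- glue: 1 − 0.60 × 0.60 = 0.640
- TIPS: 1 − 0.60 × 0.85 = 0.490
- HR: ln(0.510) / ln(0.360) = 0.66

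The chance of significance uses the Schoenfeld approximation, with expected events = 52 × (sum of the two risks). In the example this is 52 × 1.130 = 58.8 events, and Φ(√58.8/2 × |ln 0.66| − 1.96) is about 0.36.

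No true effect on non-bleeding complications (HR 1.00):

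| Rebleeding, glue vs TIPS | q, both arms | Any, glue | Any, TIPS | HR | Chance of significance for TIPS |
|---|---|---|---|---|---|
| 40% vs 15% | 40% | 64.0% | 49.0% | 0.66 | 36% |
| 40% vs 15% | 60% | 76.0% | 66.0% | 0.76 | 22% |
| 30% vs 10% | 40% | 58.0% | 46.0% | 0.71 | 24% |
| 30% vs 10% | 60% | 72.0% | 64.0% | 0.80 | 15% |
| 20% vs 5% | 40% | 52.0% | 43.0% | 0.77 | 15% |
| 20% vs 5% | 60% | 68.0% | 62.0% | 0.85 | 10% |

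Without the rebleeding component, the chance of a significant result for TIPS would be 2.5%.

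True excess of non-bleeding complications with TIPS:

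| q, glue vs TIPS | True HR | Any HR, rebleeding 40% vs 15% | 30% vs 10% | 20% vs 5% |
|---|---|---|---|---|
| 40% vs 50% | 1.36 | 0.84 | 0.92 | 1.01 |
| 40% vs 55% | 1.56 | 0.94 | 1.04 | 1.16 |

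The shift favours TIPS in every row.

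**The case against.** The strongest reply is that this is a matter of wording. The SAP attributes the definition to a consensus conference, and it is not wrong in itself. Secondary endpoints often share events, as liver-related death and survival do here. No sentence says that endpoint 5 is meant to exclude rebleeding. That intent is inferred from the word other in the section 6.2 heading, and a reader could take the same word as already excluding it. This stands in part: the intent is an inference, though a reasonable one given the order of the analyses. The list and the definition, applied literally, still count the rebleed, and no exclusion is written down.

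Three stronger readings are tempting and are not supported:
- A reader might infer that rebleeding is all that further decompensation adds. It also admits ascites that does not persist, so deleting the whole item would lose non-bleeding events.
- A reader might infer that a TIPS harm would disappear from the report. Encephalopathy has its own line in endpoint 5, appears again among the TIPS complications in endpoint 6, and adverse events are compared between arms (section 6.4). An excess could be offset only in the any-complication and further-decompensation lines.
- A reader might infer that all rebleeding re-enters. Only variceal hemorrhage does, whereas the primary endpoint counts upper gastrointestinal bleeding of any origin.

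The size is also open to challenge. If patients who rebleed tend to have other listed complications as well, the distortion shrinks. It also shrinks as the non-bleeding risk rises: at an assumed 80% in both arms with rebleeding of 40% versus 15%, the risks are 1 − 0.20 × 0.60 = 88% and 1 − 0.20 × 0.85 = 83%, and the HR is ln(0.17) / ln(0.12) = 0.84. Both points are fair and limit the size, but they do not change the direction.

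**Conclusion.** The point holds for one secondary endpoint. As written, a variceal rebleed alone counts in the any-complication line and in the further-decompensation line, and this tilts both towards TIPS if TIPS prevents rebleeding. Under independence and no true effect on non-bleeding complications, the any-complication HR would lie between about 0.66 and 0.85 over the assumed ranges. The lower end relies on rebleeding rates set at the SAP's composite rates. A moderate excess of non-bleeding complications could be neutralised in these two lines, but not in encephalopathy's own line. The primary endpoint, its analysis and the sample size are not affected. It is a cheap improvement worth making, not a threat to the trial's main conclusion.

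**What to change.** In section 6.1, state that the variceal-hemorrhage component of further decompensation does not count towards the any-complication composite, while its non-bleeding events still do, including ascites that does not persist. Report further decompensation as a separate line under its stated definition, labelled as including variceal rebleeding, and show it with and without that component. In section 6.2, state how a variceal rebleed is handled in the analysis of the other complications, for example that the patient stays at risk for a non-bleeding complication.

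This changes SAP wording only. Rebleeding is already collected with its date for the primary endpoint, so no new data are needed. The cost is fewer events, and so less precision, in the any-complication line. The change should be made before database lock so that it cannot appear to follow from the results.

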## **6.2 Analysis Methods**

Analyses of all endpoints will be performed on the mITT as well as the per protocol population unless specified.

## **Primary composite endpoint**

The Kaplan Meier method will be used to estimate rate of composite event over the 12-month follow-up. The composite event rates will be compared between study arms using the log-rank test. Hazard ratio for composite event rate (TIPS vs. GO) and its 95% confidence interval will be determined using a Cox proportional hazard model. In this model, a center effect will be tested as well as interaction between treatment and center. The assumption of proportional hazards will be tested using Schoenfeld residuals and if violated, the model will be fitted with a treatment-time interaction or a time-varying covariate, as appropriate.

The composite event rate at 12 months will be described according to a number of covariates including age, gender, and specific liver scores (Child-Pugh and MELD) to examine their potential effects. Each of these factors will be analyzed statistically using a Cox proportional hazard model incorporating terms for treatment strategy, the covariate and the strategy-by covariate interaction. The number of patients with composite event, estimated hazard ratios, and associated 95% confidence intervals will be calculated within each of the subgroups generated by these analyses.

Covariate			Treatment effect	P
	n	No. Events	HR - 95%CI	value
Intervention				р
Glue			Ref	
obliteration				
Early			Treatment effect	
TIPS				
Subgroup analyses				
Age				P*
<median< td="">		<median effect<="" td="">	</median>	</median<>			<median effect<="" td="">	</median>	

>median			>median effect	
Sex				P*
Male			Effect in men	
Female			Effect in women	
Child Pugh				P*
score				
В			Effect in B patients	
С			Effect in C patients	
MELD				P*
<median< td="">		<median effect<="" td="">	</median>	</median<>			<median effect<="" td="">	</median>	
>median			>median effect	
EH upon adm	niss	on		
No				
Yes				
High risk pat	ient	s (Child-Pugh	C, or Child-Pugh B with active bleeding)	
Not high			Effect in not high-risk patients	
risk				
High risk			Effect in high-risk patients	
Shock				P*
No shock			Effect in patients with shock	
Shock			Effect in patients without shock	
ACLF upon a	adm	ission†		P*
Grade 1				_
Grade 2				_
Grade 3				
Red blood cell transfusion during initial hospitalization				P*
0	)		Effect in untransfused patients	
1-2			Effect in transfused patients 1-2 RBC units	
>2			Effect in transfused patients with more than RBC units	

\* p value for interaction

The win ratio method (Pocock et al. Eur Heart J. 2012 Jan;33(2):176-82) will also be applied in order to determine the least effective procedure when giving priority to the more clinically important event (death).

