## 3.3 Sample size

The sample size is calculated with a projected rate of composite event of failure at 12 months of 15% in the group "TIPS" [estimated from Garcia Pagan, New Engl J Med 2010] versus 40% in the group « glue» [estimated from Hou, Gastrointest Endosc 2009].

A number of 52 patients in each group will achieve 80% power to detect TIPS superiority using a one-sided logrank test at a 0,050 significance level, with a proportion dropping out of both groups of 10%.

Total number of scheduled patients recruited or observations collected: 104.

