## **Section 4: Statistical Principles**

#### 4.1 Confidence Intervals and P-values

All tests will be two-sided, with p values of less than 0.05 denoting statistical significance. 95% confidence interval will be used to report effect estimates of secondary endpoints.

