## **5.3 Baseline Patient Characteristics**

The description and initial comparison of randomized groups will focus on:

- Patient information: demographic characteristics, clinical exams, place of support, medical history, radiological exams, diagnosis of cirrhosis, cause and complications of cirrhosis, hepatocellular carcinoma, and concomitant treatments
- Endoscopic characteristics of initial bleeding: endoscopic condition, lesion responsible for bleeding, pre-existing treatment
- Biological results at admission: virology, hematology, blood biochemistry, arterial blood gas, bacteriology, ascites puncture, plasma
- Scores: Child-Pugh, MELD, MADDREY

Quantitative variables will be in the form of a table showing the number of values and the number of missing data, the mean and median, standard deviation, coefficient of variation, the minimum and maximum for each group and for the overall population.

Categorical variables will be in the form of a table revealing the number of values and the number of missing data, the percentage of each category and the confidence intervals for each group and for the overall population.

Continuous variables will be compared using Student's t-test or the Mann-Whitney test, as appropriate. Categorical variables will be compared using the Chi-squared test or Fisher's exact test, as appropriate.

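### The primary hazard ratio names no baseline severity term although MELD is collected; prespecifying one is a modest efficiency and prespecification gain, not the repair of an error.

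*SAP*

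**What the plan says.** **Primary endpoint (SAP 6.2, Primary composite endpoint).** The arms are compared by a log-rank test, with no covariate or stratum named. For the estimate, "Hazard ratio for composite event rate (TIPS vs. GO) and its 95% confidence interval will be determined using a Cox proportional hazard model". Centre and its interaction with treatment are to be tested in that model. No baseline prognostic covariate is named.

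**Where MELD appears.** The baseline list in 5.3 includes "Scores: Child-Pugh, MELD, MADDREY". In 6.2, MELD and Child-Pugh enter only separate models, one covariate at a time, each with its interaction with treatment. These serve the subgroup table and do not give an overall hazard ratio adjusted for severity.

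**Randomisation (3.2).** Centre is the only stratification factor.

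**Secondary endpoints (6.2).** For rebleeding, the association with study arm "will be tested using univariate and multivariate Cox models". Similar wording covers liver-related death and the other complications of cirrhosis. No covariates are listed for the multivariate models.

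**Missing data (6.3).** As a general rule missing values stay missing, and only observed values are analysed.

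**The concern.** With 52 patients per arm, the arms can differ in MELD by chance. If MELD predicts death or rebleeding, that difference passes into an unadjusted hazard ratio, and with fewer than 30 events the shift can be noticeable. The plan has no prespecified answer. If an imbalance appears, any adjustment of the primary result would be chosen after the data are seen, in an open-label trial. The secondary endpoints do get multivariate models, but with covariates left open, so there too the choice could follow the results.

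At stake are an estimate protected from one foreseeable source of chance imbalance, a fixed rule in place of a later choice, and possibly a little power.

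**Working it through.** **Inputs from the SAP.** Section 3.3 gives a "projected rate of composite event of failure at 12 months of 15% in the group" receiving TIPS "versus 40% in the group" receiving glue, with 10% dropout. It states: "A number of 52 patients in each group will achieve 80% power", "using a one-sided logrank test at a 0,050 significance level". Section 4.1 sets the analysis level: "All tests will be two-sided, with p values of less than 0.05 denoting statistical significance". The power figures below are two-sided, as in 4.1. The mismatch between 3.3 and 4.1 is a separate matter.

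**1. The plan's own figure.** Two proportions, one-sided 0.05, 80% power, mean risk (0.40 + 0.15)/2 = 0.275:

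- n = [1.645 × √(2 × 0.275 × 0.725) + 0.842 × √(0.40 × 0.60 + 0.15 × 0.85)]² / 0.25² ≈ 38.4.
- With continuity correction: (38.4/4) × [1 + √(1 + 4/(38.4 × 0.25))]² ≈ 46.1, so 47 per arm.
- Dropout: 47 × 1.10 = 51.7, so 52; or 47/0.90 = 52.2, so 53.

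The stated 52 is therefore reproduced, though by a two-proportion formula. A log-rank formula with hazard ratio ln(0.85)/ln(0.60) = 0.318 gives, one-sided, 49 per arm (Freedman, 24 events) or 39 (Schoenfeld, 19 events).

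**2. Expected events.** With complete follow-up, 52 × (0.40 + 0.15) = 28.6. If dropouts contribute no events, 28.6 × 0.90 = 25.7. In simulation with 10% dropout spread over the year, 27.3.

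**3. Chance imbalance in MELD.** The SD of the standardised mean difference is √(2/52) = 0.196, so the 95% range is ±1.96 × 0.196 = ±0.38 SD. An imbalance at that limit multiplies the crude hazard ratio by about h^0.38, where h is the hazard ratio per SD of MELD:

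| Assumed h | Factor |
|---|---|
| 1.25 | 1.09 |
| 1.5 | 1.17 |
| 2.0 | 1.31 |
| 2.5 | 1.42 |

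**4. Typical shift in the log hazard ratio.** Counting only the baseline mean difference, the SD is 0.196 × ln(1.5) = 0.08 to 0.196 × ln(1.8) = 0.12. In simulation, the fitted adjusted and unadjusted log hazard ratios differ by an SD of 0.10 to 0.15 over the same range. The simulated figure is larger because it also contains the error in estimating the MELD coefficient and the changing mix of patients still at risk. Against an unadjusted standard error of about 0.435, it is 0.10/0.435 = 23% to 0.15/0.435 = 34% of one standard error.

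**5. Power.** Simulation with 52 per arm, exponential times, 12-month risks held at 40% and 15%, 10% dropout, 3,000 runs per row, two-sided 0.05:

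| h per SD | Log-rank | Adjusted Cox, Wald | Adjusted Cox, likelihood ratio |
|---|---|---|---|
| 1.0 | 81.3% | 79.6% | 81.4% |
| 1.25 | 81.2% | 80.4% | 82.5% |
| 1.5 | 81.3% | 81.5% | 83.2% |
| 2.0 | 81.2% | 84.7% | 86.1% |
| 2.5 | 81.2% | 88.7% | 89.7% |

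With the Wald test the gain over the log-rank test is 81.5 − 81.3 = 0.2 points at h = 1.5 and 84.7 − 81.2 = 3.5 points at h = 2.0. If MELD is not prognostic the loss is 81.3 − 79.6 = 1.7 points, and none with the likelihood-ratio test. Larger gains need h = 2.5, beyond the range assumed here.

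**6. Where the gain comes from.** The median standard error of the log hazard ratio does not fall: 0.434 to 0.437 unadjusted, 0.437 to 0.447 adjusted (h from 1.0 to 2.5). The adjusted model instead targets a conditional hazard ratio further from 1: 0.309 at h = 1.5 and 0.290 at h = 2.0, against 0.318 unadjusted.

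**7. Validity of the plan as written.** With no treatment effect, the two-sided log-rank test rejected in 4.6% (MELD not prognostic) and 5.2% (h = 2.0) of 2,000 runs.

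**The case against.** The strongest objection is that nothing in 6.2 is wrong. A log-rank test and an unadjusted Cox hazard ratio are sound in a randomised trial, and the test keeps its size. That stands. A reader might infer that the primary analysis is in error or biased; the SAP does not support that.

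A reader might also infer that adjustment recovers worthwhile power at no cost. This fails on three counts. The trial's comparison is the log-rank test, so adding MELD to the Cox model alone leaves the power of that comparison unchanged. The gain is small at the planned risks and rests on a prognostic strength that the SAP never states. The adjusted hazard ratio is conditional on MELD, a different quantity, and its standard error is no smaller.

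Two further inferences go beyond the text. Section 6.2 proposes to examine potential effects of the liver scores; it does not assert that they affect the composite. The SAP also gives no split between deaths and rebleeds, so the share of events that severity might drive is unknown.

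Finally, the choice of MELD over Child-Pugh is a judgement, since the SAP names both. One continuous term suits the small number of events; the important step is to name it in advance.

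**Conclusion.** The point holds as an efficiency and prespecification improvement. The primary hazard ratio names no severity term, MELD is available at baseline, and stratification does not cover it. With about 27 expected events and an assumed hazard ratio of 1.5 to 1.8 per SD of MELD, adjustment moves the log hazard ratio by an SD of about 0.10 to 0.15, a factor of e^0.10 = 1.11 to e^0.15 = 1.16 on the hazard ratio. Using the adjusted Cox test in place of the log-rank test changes power by roughly 0 to 4 points, and costs 1 to 2 points (Wald test) if MELD is not prognostic. If the log-rank test stays confirmatory, the benefit is limited to an estimate protected from chance MELD imbalance. All these sizes depend on the planned 15% and 40% risks, 10% dropout and the assumed strength of MELD.

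**What to change.** - **6.2, primary endpoint:** take the hazard ratio and 95% confidence interval from a Cox model with arm and inclusion MELD as one continuous term. Report the unadjusted hazard ratio beside it.
- **6.2, confirmatory test:** state whether the log-rank test or the adjusted Cox test decides the trial. Any power gain exists only under the second choice.
- **6.3:** add an exception so that a missing baseline MELD is filled by single imputation. Under the present rule that patient would drop out of the adjusted model.
- **6.2, secondary Cox analyses:** use the same model, arm plus MELD, where multivariate models are now promised without covariates.

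The cost is a few sentences before database lock, with no extra patients or data items. The hazard ratio becomes conditional on MELD and its standard error does not fall, which is why the unadjusted figure should stay in the report. Whether to drop the baseline significance tests in 5.3 is a separate matter and does not affect the primary result.
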